6.5.2.3 Pneumonitis

Section 2.3.2.1 provides a summary of pembrolizumab safety profile. Management guidelines for patients experiencing pneumonitis are as follows:

Grade 1 pneumonitis

- No specific therapy required, close monitoring of lung function and imaging

Grade 2 pneumonitis

- Hold MGA271 and pembrolizumab or MGA012
- Begin corticosteroids: 1 to 2 mg/kg of oral prednisone or equivalent, per day divided twice daily
- Taper over 4 weeks as clinically indicated

- Resume MGA271 and pembrolizumab or MGA012 administration at next scheduled dose, if:
 - Pneumonitis resolves to \leq Grade 1 within 3 days with or without treatment

Grade 3 and 4 pneumonitis

- Hospitalize
- Permanently discontinue MGA271 and pembrolizumab or MGA012
- Initiation of maximal supportive care including IV corticosteroids, suggest methylprednisolone at 2- 4 mg/kg/day divided twice daily. Higher doses may be used in consultation with the Sponsor's medical monitor
- If no response to corticosteroid therapy is observed within 3-5 days, consider adding immune suppression therapy (i.e., infliximab, etc.)

6.5.2.4 Dermatologic Toxicity

Section 2.3.2.1 provides a summary of pembrolizumab safety profile. Management guidelines for patients experiencing dermal toxicities are as follows:

In general, Grade 1 or 2 skin reactions can be treated symptomatically with low-dose topical corticosteroids (betamethasone 0.1% or hydrocortisone 1%) or with antihistamines, such as diphenhydramine. Persistent Grade 1 or 2 rash should be managed with higher dose topical corticosteroids and/or oral prednisone (1-2 mg/kg/day) if there is no improvement with topical therapies or the rash is associated with other dermal toxicities such as pruritus. Grade 3 or 4 rashes require initiation of oral corticosteroids (oral prednisone 1 – 2 mg/kg/day) and temporary holding of study drugs with Grade 3 toxicity and permanent discontinuation for Grade 4 toxicity. Grade 3 skin toxicity that does not resolve to \leq CTCAE Grade 2 within 14 days of initiation of oral corticosteroids requires permanent discontinuation of study therapy. Strong consideration should be given to start IV corticosteroids (methylprednisolone 1-2 mg/kg/day) for Grade 4 dermatologic toxicities with tapering on resolution to $<$ Grade 2 over 30 days.

6.5.2.5 Nephritis/Renal Failure

Section 2.3.2.1 provides a summary of pembrolizumab safety profile. Management guidelines for patients experiencing nephritis/renal failure are as follows:

Grade 1 nephritis

- No specific therapy required, close monitoring of renal function

Grade 2 nephritis

- Hold MGA271 and pembrolizumab or MGA012

- Consider nephrology consultation and renal biopsy to confirm interstitial nephritis.
- Begin corticosteroids: 1 to 2 mg/kg of oral prednisone or equivalent, per day divided twice daily
 - Taper over 4 weeks as clinically indicated
- Resume MGA271 and pembrolizumab or MGA012 administration at next scheduled dose, if:
 - Nephritis resolves to \leq Grade 1 within 14 days with or without treatment

Grade 3 and 4 nephritis

- Consider hospitalization, nephrology consultation and renal biopsy to confirm interstitial nephritis
- Begin corticosteroids: 2 to 4 mg/kg of oral or IV prednisone or equivalent, per day divided twice daily
 - Taper over 4 weeks as clinically indicated
- Permanently discontinue MGA271, pembrolizumab, or MGA012 for Grade 3/4 nephritis.

6.5.2.6 Immune-Mediated Endocrinopathies

Section 2.3.2.1 provides a summary of pembrolizumab safety profile. Management guidelines for patients experiencing endocrinopathies are as follows:

6.5.2.6.1 Hypophysitis

In cases of symptomatic (Grade 2 or 3) hypophysitis documented on MRI:

- Hold pembrolizumab or MGA012 and MGA271
- Consult endocrinologist
- Consider hospitalization
- Begin short course of high dose IV corticosteroids: e.g. methylprednisolone 2-4 mg/kg IV (or equivalent) divided twice daily
- Initiate hormonal replacement as indicated
- Pembrolizumab or MGA012 and/or MGA271 may be resumed as allowed by protocol when
 - Endocrinopathy is controlled with appropriate replacement therapy

- Corticosteroid dose reduced to \leq 10 mg prednisone or equivalent per day
- Repeat brain MRI as clinically indicated

Discontinue MGA271 and pembrolizumab or MGA012 for Grade 4 hypophysitis

6.5.2.6.2 Thyroid Toxicity

Hyperthyroidism/Hypothyroidism:

There have been no reported cases of endocrine toxicities in the Phase 1 dose escalation and expansion trial of MGA271.

Thyroid disorders can occur at any time during treatment with pembrolizumab. Monitor patients for changes in thyroid function (at the start of treatment, periodically during treatment, and as indicated based on clinical evaluation) and for clinical signs and symptoms of thyroid disorders. Isolated hypothyroidism may generally be managed with replacement therapy without treatment interruption and without corticosteroids and a suggested treatment guideline for hyperthyroidism is described below:

Grade 1 hyperthyroidism

- No specific therapy required

Grade 2 hyperthyroidism

- Hold pembrolizumab or MGA012 and MGA271
- Resume pembrolizumab or MGA012 and/or MGA271 if stable on hormone replacement therapy (if necessary)

Grade 3 or 4 hyperthyroidism

- Hold pembrolizumab or MGA012 and/or MGA271
- Consider hospitalization and consulting endocrinologist
- Initiate hormonal replacement as necessary

May consider restarting pembrolizumab or MGA012 and MGA271 with complete resolution or stable on hormone replacement therapy

6.6 Method of Assigning Patients to Treatment Groups

Patients will be assigned sequentially to the dose escalation cohorts and cohort expansion portions of the study.

6.7 Blinding

This is an open-label study and no blinding will be employed.

6.8 Concomitant Therapy

MGA271, pembrolizumab, and MGA012 are the only cancer drugs to be administered routinely in this study. No concomitant anti-cancer therapy will be given.

All concomitant medications and blood products administered during the patient's participation in the study until the post treatment follow-up visit must be recorded in the source document and on the electronic Case Report Form (eCRF). All changes in infusions, including interruptions and their duration as well as reductions in rate and duration must be recorded.

The following rules concerning concurrent treatment(s) will apply in this study:

- Any other anti-neoplastic therapies including but not limited to chemotherapy or other small molecules, biologics, or radiotherapy are not allowed. For patients who require palliative radiotherapy (i.e., cumulative dose less than 3000 rads, limited field of distribution) for reasons other than disease progression, therapy with MGA271 and pembrolizumab may be interrupted for up to 4 weeks. Palliative radiotherapy may not be given concurrently with either MGA271 or pembrolizumab or MGA012. Treatment with palliative therapy should be initiated at least 24 hours after receiving either MGA271 or pembrolizumab or MGA012, and re-initiation of MGA271 or pembrolizumab or MGA012 can begin one day after the completion of palliative radiotherapy if there were no complications associated with the radiotherapy. Palliative radiotherapy fields also should not overlap tumor lesions that have previously been designated as target lesions. In the event that this is medically necessary for palliative purposes, the patient may continue on study, but will no longer be evaluable for objective response from the time palliative radiotherapy is initiated.
- Patients may not receive other investigational drugs during the period of study participation.
- Because MGA271, pembrolizumab, and MGA012 have a mechanism of action dependent upon the engagement of T lymphocytes, the use of corticosteroids should be limited to the extent possible. Chronic doses of corticosteroids in excess of 10 mg daily of prednisone or equivalent is prohibited other than for the management of drug-related adverse experiences. Steroids may be employed in the treatment of suspected MGA271- or pembrolizumab- or MGA012-associated immune-inflammatory or autoimmune AEs in consultation with the Sponsor.
- The use of other immuno-suppressive agents is prohibited, unless they are being used to treat an adverse event.
- Use of granulocyte colony stimulating factor, granulocyte-macrophage colony stimulating factor or other growth factors is prohibited.

- Live vaccines within 4 weeks prior to the first dose of MGA012 and while participating in the study are prohibited. Examples of live vaccines include, but are not limited to, the following: measles, mumps, rubella, chicken pox, yellow fever, rabies, BCG, and typhoid (oral) vaccine. Seasonal influenza vaccines for injection are generally recombinant vaccines and are allowed any time after the DLT period is completed. However, intranasal influenza vaccines (e.g., FluMist®) are live attenuated vaccines and are not allowed. Similarly, Shingrix® vaccine for shingles is permitted after the DLT period, but Zostavax® is prohibited.

Patients may receive the following concurrent therapy:

- Antiemetics, antidiarrheals, anticholinergics, antispasmodics, antipyretics, antihistamines, analgesics, antibiotics and other antimicrobials, histamine receptor antagonists or proton pump inhibitors, and other medications intended to treat symptoms or signs of disease.
- Transfusions such as red blood cells and platelets are permitted to treat symptoms or signs of anemia or thrombocytopenia and should be documented on the concomitant medication form.
- Use of bisphosphonates or receptor activator of nuclear factor kappa-B ligand (RANK-L) inhibitors is allowed

6.9 Restrictions

6.9.1 Prior Therapy

Prior therapy restrictions are described in the inclusion/exclusion criteria specified in **Section 5**.

6.9.2 Fluid and Food Intake

There are no requirements for fasting and no restrictions for fluid and food intake by the patients during the study, although it is recommended that, to the extent possible, patients have a fluid intake of \geq 2 liters on days associated with PK sampling, and that electrocardiograms will be obtained pre-meal.

6.9.3 Patient Activity Restrictions

There are no restrictions on patient activities and no requirement for patient confinement during the study.

6.10 Treatment Compliance

MGA271 and pembrolizumab will be administered by healthcare professionals under the supervision of the Investigators. Records of MGA271 and pembrolizumab dose calculation, administration, and dosing regimen will be accurately maintained by site staff. The monitor will review dose calculation, administration and regimen as well as medication accountability during investigational site visits and at the completion of the study.

6.11 Packaging and Labeling

6.11.1 MGA271

MGA271 will be supplied in open-label, single-dose vials. All investigational product will be labelled with a minimum of the protocol number, directions for use, storage conditions, expiry date (if applicable), batch number, the statements “For clinical trial use only,” and/or “CAUTION: New Drug – Limited by Federal (United States) Law to Investigational Use,” and the Sponsor's name and address. Please see the Pharmacy Manual for detailed information about the packaging and labeling of the study drug.

6.11.2 Pembrolizumab

Pembrolizumab will be obtained by the site from commercial supply for patients with melanoma. Pembrolizumab will be provided in the commercial packaging. Please see the Pharmacy Manual for detailed information about the packaging and labeling of pembrolizumab.

6.11.3 MGA012

MGA012 will be supplied

Please see the Pharmacy Manual for detailed information about the packaging and labeling of the study drug.

6.12 Storage and Accountability

6.12.1 MGA271

The vials containing study drug should be and must not be frozen or shaken. Protect from sunlight. To ensure compliance with storage conditions, temperature logs will be maintained.

The Investigator or his/her designee is required to maintain accurate drug accountability records. A binder containing instructions and the required accountability documentation will be provided to the Investigator or his designee. When the study is completed, copies of study drug accountability records must be sent to the Sponsor. The original drug accountability

records must be maintained with the rest of the documentation in accordance with **Section 10.1** of the protocol.

Additional details regarding storage, handling, and accountability can be found in the Pharmacy Manual.

6.12.2 Pembrolizumab

Pembrolizumab is marketed as KEYTRUDA by Merck & Co., Inc., Whitehouse Station, NJ 08889.

Pembrolizumab is supplied in the following configurations:

- KEYTRUDA (pembrolizumab) injection (lyophilized powder): carton containing one 50 mg single-use vial (NDC 0006-3029-02).
- KEYTRUDA (pembrolizumab) injection (solution): carton containing one 100 mg/4 mL (25 mg/mL), single-use vial (NDC 0006-3026-02)

Store vials under refrigeration at 2°C to 8°C (36°F to 46°F) in original carton to protect from light. Do not freeze. Do not shake.

6.12.3 MGA012

Vials containing MGA012 should be stored upright

in an appropriate, locked room accessible only to pharmacy personnel, the Investigator, or duly designated personnel. To ensure compliance with storage conditions, temperature logs will be maintained. Vials should be protected from light during storage and should not be shaken or frozen. Standard laboratory practices should be used for avoidance of contact.

6.12.4 Accounting for the Materials

Accurate accounting of all study medication must be maintained. The Investigator agrees to keep an inventory of study drugs using the institution's drug accountability logs or logs provided by MacroGenics. Drug disposition records must be kept in compliance with applicable guidelines and regulations.

A Pharmacy Manual will be provided to the Investigator or designee. When the study is completed, copies of all study drug accountability records must be provided to the Sponsor. Original drug accountability records must be maintained with the rest of the documentation for inspection by the study monitors. Additional details regarding storage, handling, and accountability can be found in the Pharmacy Manual.

6.13 Investigational Product Disposition at End of Study

Upon completion or termination of the study, all unopened vials of study medication must be returned to MacroGenics or its representative, unless the site has received written

authorization from MacroGenics to destroy study drug at the site. All drug returns to MacroGenics or its representative must be accompanied by the appropriate documentation and be clearly identified by protocol number and study site number on the outermost shipping container. If MacroGenics approves the destruction of drug at the site, the Investigator must ensure arrangements are made for proper disposal and that appropriate records of disposal are documented and maintained and copies provided to the Sponsor.

In Editing

7 STUDY PROCEDURES

This section provides a general description of the procedures and assessments associated with this study. Time and Events Schedule ([Appendix 1](#)) details the schedule of assessments by study day.

Note: On days where multiple procedures are required at the same time point, the PK sample should be collected first.

7.1 Informed Consent

The Investigator is responsible for ensuring that the patient or his/her legal representative provides informed consent prior to performing any study related assessments, evaluations, or procedures. Informed consent for this study must be provided by signing an Institutional Review Board (IRB)/Independent Ethics Committee (IEC)-approved informed consent document (Consent for Study Participation). A copy of the relevant signed informed consent document must be provided to the patient and the original maintained according to institutional procedures. The patient's medical records will include documentation of the informed consent process. Informed consent will be obtained prior to any study screening procedures being performed.

7.2 Medical History

A complete medical history should be obtained during the screening visit. All concurrent medical conditions in the last 60 days and any significant medical conditions (e.g., hospitalizations, surgeries, prior cancer history) should be collected. During the screening period (prior to first dose of pembrolizumab, MGA012, or MGA271), any untoward event that occurs should be recorded as medical history and not as an adverse event, unless it is due to a protocol-related procedure. Thereafter (i.e., after the time of study drug administration), any untoward event should be collected as an AE.

7.3 Prior and Concomitant Medications

All concomitant medications and blood products administered during the patient's participation in the study until the End of Treatment Visit must be recorded in the source document and on the eCRF.

Prior courses of systemic cancer therapy (e.g., chemotherapy, immunotherapy, etc.) will be documented in the medical records and on the eCRF.

7.4 Physical Examination

The Investigator will perform physical examination of all patients. Physical examination will include height (screening only), weight, and examination of skin, HEENT (head, eyes, ears, nose, and throat), lymph nodes, heart, chest, lungs, abdomen, extremities, and neurologic system as specified in [Appendix 1](#).

Weight will be measured during screening, Day 1, and then before each dose of pembrolizumab, MGA012, or MGA271.

7.5 Vital Signs

Vital signs include temperature, pulse, blood pressure, and respiratory rate and are obtained as specified in **Table 8** for MGA271 and pembrolizumab or **Table 9** for MGA271 and MGA012.

7.6 Clinical Laboratory Tests

Blood and urine samples will be collected at the times specified in **Appendix 1**. Hematology, chemistry, pregnancy, urinalysis, coagulation time, and endocrine evaluation tests will be performed locally. Safety labs should be performed and reviewed before study drug administration.

Please consult the Laboratory Manual for specific directions on collection and processing samples.

7.6.1 Laboratory Parameters

Clinical laboratory tests to be performed locally will include the following:

Table 4 Clinical Laboratory Tests

Pregnancy test: Urine Human chorionic gonadotropin (hCG) Hematology: Hematocrit (Hct) Hemoglobin (Hgb) Mean corpuscular hemoglobin (MCH) Mean corpuscular hemoglobin concentration (MCHC) Mean corpuscular volume (MCV) Platelet count Red blood cell (RBC) count White blood cell (WBC) count with differential counts Serum Chemistry: Albumin (ALB) Alkaline phosphatase (ALK-P) Alanine aminotransferase (ALT; SGPT) Aspartate aminotransferase (AST; SGOT) Bicarbonate Blood urea nitrogen (BUN) Calcium (Ca) Chloride (Cl) Creatinine Glucose Magnesium Phosphorus Potassium (K) Sodium (Na) Total protein Uric acid	Special Chemistry: Amylase Lipase Bilirubin (Total and Direct) Coagulation: Prothrombin time (PT) Activated Partial Thromboplastin Time (APTT) Endocrine tests: Free thyroxine (T4) Thyroid-stimulating hormone (TSH) Urinalysis: Appearance Bilirubin Color Glucose Ketones Microscopic examination of sediment Nitrite Occult blood pH Protein Specific gravity
--	--

Other tests (PK, anti-drug antibody [ADA], cytokines, determination of leukocyte subsets, evaluation of T cell activation status, expression of markers of T cells, determination of T cell infiltration, and tumor B7-H3 expression) will be carried out at Sponsor-specified central laboratories (refer to the Laboratory Manual).

7.6.2 Sample Collection, Storage, and Shipping

Clinical laboratory testing described in **Section 7.6.1** will be performed locally. Details on local and central laboratory specimen collection, storage, and shipping will be provided in the Laboratory Manual.

7.7 **Electrocardiography**

Twelve-lead electrocardiograms (ECGs) (in triplicate, approximately 1 minute apart) will be obtained according to the ([Appendix 1](#)) in order to evaluate the potential cardiac effects of the combination of MGA271 and pembrolizumab and of MGA271+MGA012, including QT interval. There are no requirements for fasting and no restrictions for fluid and food intake by the patients during the study, although it is recommended that, to the extent possible, ECGs be obtained pre-meal at approximately the same time of the day to minimize diurnal variations. However, this may not be possible because of infusion times and clinic logistics.

To account for intrinsic variability, all ECGs should be obtained in triplicate (3 ECGs per time point at approximately 1-minute intervals). Central interpretation will be used for data analysis purposes; note for Cohort 4 only, ECGs will be read locally. ECGs are to be obtained as specified in [Table 8](#) for MGA271 and pembrolizumab and in [Table 9](#) for MGA271 and MGA012.

7.8 **Safety Assessments**

7.8.1 **Criteria for Evaluation**

- The safety assessment will be based on the evaluation of treatment-emergent AEs that occur from the time of initiation of administration of either study drug through the End of Treatment Visit or 28 days after the last dose of study drug (whichever is later) and will be determined based on signs, symptoms, physical examination findings and/or laboratory test results from enrolled patients as appropriate.
- AEs and SAEs will be collected from the time the patient receives the first dose of study drug until the End of Treatment visit or 28 days after the last dose of study drug (whichever is later). Protocol-related AEs and SAEs will be collected from the time the patient has consented to study participation.
- AEs reported between the time the patient signed the informed consent and the administration of the first dose of study drug will be captured as medical history.
- SAEs considered related to study drug may be reported at any time, even after the patient's final visit.
- Progression of the underlying neoplasm resulting in hospitalization or death (e.g., patient hospitalized for or dies from progressive disease [PD] only, without any other SAE) will be documented as an antitumor activity outcome and not as an SAE. If an SAE occurs in a patient and it is unclear whether the event is related to PD, the SAE should be reported.
- The reporting of laboratory/vital signs abnormalities as both laboratory findings and AEs should be avoided. They should not be reported as AEs unless any one of the following are met:
 - Any criterion for an SAE is fulfilled

- The laboratory/vital signs abnormality causes the patient to discontinue from the study treatment
- The laboratory/vital signs abnormality causes the patient to interrupt the study treatment
- The laboratory/vital signs abnormality causes the patient to modify the dose of study treatment
- The laboratory/vital signs abnormality requires intervention

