2.3.1.1 Safety

2.3.1.1.1 Nonclinical Data

2.3.1.1.2 Clinical Trial Experience

MGA271 is currently being evaluated in patients with cancer in 4 ongoing, Phase 1, MacroGenics-sponsored clinical studies. Clinical trial experience is presented for MGA271+pembrolizumab combination therapy for the current study (CP-MGA271-03) and MGA271 monotherapy for Study CP-MGA271-01. Data from remaining 2 studies are not included, 1 explores MGA271 treatment in a pediatric population and the other explores combination MGA271 and ipilimumab treatment.

Safety

As of the cutoff date of 13 April 2019, safety data are available for 133 patients exposed to MGA271+Pembrolizumab in Study CP-MGA271-03 and for 179 patients exposed to MGA271 in Study CP-MGA271-01. A discussion of safety for each study is presented below.

Study CP-MGA271-03

Adverse events considered related to MGA271+pembrolizumab treatment were reported in 116 patients (87.2%). The most common treatment-related adverse events (TRAEs) reported in $\geq 5\%$ of patients exposed to MGA271+pembrolizumab in decreasing order of frequency were as follows: infusion-related reaction (54.1%); fatigue (27.8%); nausea (9.8%); pyrexia (9.0%); lipase increased (8.3%); arthralgia (7.5%); events of diarrhea, rash maculo-papular, and decreased appetite (6.8%, each); events of hypothyroidism and pneumonitis (6.0%, each); events of chills, anemia, lymphocyte count decreased, and pruritus (5.3% each). Greater than or equal to Grade 3 TRAEs were reported in 38 patients (28.6%). Of these, the most commonly reported in $\geq 5\%$ of patients was infusion-related reaction (6.8%) and lipase increased (6.0%).

Forty-eight patients (36.1%) experienced at least 1 serious adverse event (SAE). The most common SAEs, reported in $\geq 2\%$ of patients in decreasing order of frequency were: infusion-related reaction (6.8%), pneumonitis (4.5%), and dyspnea (2.3%). Twenty-three patients (17.3%) experienced SAEs considered related to MGA271+pembrolizumab; the majority of these events were \leq Grade 3 in severity (20/23 patients [87%]). The most common SAEs considered related were infusion-related reaction (6.8%) and pneumonitis (4.5%). Fourteen patients (10.5%) experienced at least 1 \geq Grade 3 SAE that was considered related to MGA271+pembrolizumab; with the exception of infusion-related reaction (6 patients [4.5%]) and pneumonitis (3 patients [2.3%]), the events were singularly reported.

Study CP-MGA271-01

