Clinical Laboratory Changes: Safety laboratory assessments will be carried out locally and evaluated by the Investigator to ensure patient safety. The Investigator is responsible for reviewing the results of all laboratory tests as they become available. Laboratory tests will be graded according to CTCAE v 4.03. Laboratory values that fall outside of a clinically accepted reference range or values that differ significantly from previous values must be evaluated by the Investigator for clinical significance. The Investigator may repeat the laboratory test or request additional tests to verify the results of the original laboratory tests. If the Investigator determines the laboratory value is an abnormal change from baseline and is of clinical significance for that patient, it is considered an AE. Generally, Grade 1 laboratory findings need not be reported as AEs unless clinically significant. The Investigator will evaluate laboratory findings of \geq Grade 2 or higher classification to determine their clinical significance and if an AE has occurred. Consistent with the CTCAE designation of Grade 3 events as severe or medically significant and Grade 4 events as life-threatening, Grade 3 and Grade 4 laboratory findings should be reported as AEs or SAEs, as appropriate. Grade 2 laboratory findings may be reported as AEs if, in the opinion of the Investigator, the event exhibits clinical significance. If clinically relevant abnormal laboratory values are associated with clinical symptom(s), or consistent with a diagnosis, the diagnosis should be reported as the AE (e.g., hemoglobin 9 g/dL in an adult female = anemia). If these clinically relevant abnormal laboratory values do not result in a diagnosis, the test result or finding should be reported as the AE assuming that it does not represent a laboratory error. Repeat testing may be indicated. Such laboratory values should generally be recorded as “increased” or “decreased” (e.g., change from baseline hemoglobin of 13 g/dL to 11 g/dL = hemoglobin decreased).

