6.7.2 Laboratory Values

Summaries of laboratory values will display descriptive statistics for numerically quantified labs. Absolute values and changes from baseline will be summarized and grouped by lab panel (e.g., hematology, blood chemistry, and urinalysis). For each panel, the data will be displayed by lab parameter and visit. Shift tables may be generated.

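### Two laboratory reporting rules conflict, so the Grade 3 or higher AE summaries can vary by site; DLT counts are not affected

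*Protocol*

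**What the plan says.** **First rule.** Protocol Section 7.8.1, repeated in the synopsis under Safety Assessments, discourages recording a laboratory or vital-sign abnormality both as a finding and as an AE. It then sets a bar: "They should not be reported as AEs unless any one of the following are met". The five triggers are:

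- an SAE criterion ("Any criterion for an SAE is fulfilled");
- discontinuation of study treatment;
- interruption ("The laboratory/vital signs abnormality causes the patient to interrupt the study treatment");
- modification of the dose;
- need for intervention ("The laboratory/vital signs abnormality requires intervention").

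Neither CTCAE grade nor clinical significance is on the list.

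**Second rule.** Protocol Section 7.8.6, under Clinical Laboratory Changes, says "Grade 3 and Grade 4 laboratory findings should be reported as AEs or SAEs, as appropriate". It also counts as an AE any abnormal change that the investigator judges clinically significant in that patient, which brings in lower grades. SAP 5.2.2 repeats both statements.

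**Analyses that depend on the rules.** Protocol Section 9.4.1 and SAP 6.7.1 plan tables of Grade 3 or higher AEs and of drug-related Grade 3 or higher AEs, built from reported treatment-emergent AEs. Laboratory values are summarised separately by parameter and visit. For graded change, SAP 6.7.2 says only "Shift tables may be generated".

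**The concern.** Both rules are current text, both deal specifically with laboratory abnormalities, and neither refers to the other or sets an order of precedence. The synopsis lists about 30-40 institutions, and each could reasonably follow either rule.

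Safety and tolerability are the primary objective, and Section 7.8.1 bases the safety assessment on treatment-emergent AEs. A site that follows Section 7.8.1 would leave out some Grade 3 and 4 laboratory events that a site following Section 7.8.6 would record. A table that pools the two would mix two definitions. The other planned outputs are not certain to recover the missing events, because summaries by visit do not count patients by worst grade and shift tables are optional.

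**Working it through.** **Step 1. Where the rules differ.** Take a Grade 3 or 4 laboratory value and apply each rule.

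| Feature of the finding | Section 7.8.1 and synopsis | Section 7.8.6 and SAP 5.2.2 |
|---|---|---|
| Meets an SAE criterion | Report | Report |
| Leads to discontinuation, interruption or dose modification | Report | Report |
| Requires intervention | Report | Report |
| None of these | Do not report | Report |

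Only the last row conflicts. Below Grade 3 there is a parallel gap for a clinically significant value with no action taken. It affects the all-grade AE tables but not the Grade 3 or higher tables.

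**Step 2. Does it reach the dose decision?** Section 4.2 bases DLTs on drug-related AEs or laboratory abnormalities, so a qualifying laboratory value counts whether or not it was entered as an AE. DLT counts cannot stand in for the AE tables, however. The DLT window is the first cycle only. Section 4.2.1 excludes Grade 3 or higher lymphopenia, and Section 4.2.2 excludes Grade 3 amylase or lipase elevation without evidence suggestive of pancreatitis.

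**Step 3. Reproduce the protocol's interim figures.** Section 2.3.1.1.2 gives, for 133 patients on MGA271 plus pembrolizumab, 38 patients with a related AE of Grade 3 or higher (28.6%), and lipase increased at that severity in 6.0%.

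- 38/133 = 28.6%, which agrees. The exact 95% CI is 21.1% to 37.0%.
- The only count out of 133 that rounds to 6.0% is 8, since 8/133 = 6.0%.

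**Step 4. Illustrate the effect, for lipase alone.** Let d be the number of those 8 patients who met none of the five triggers and had no other related Grade 3 or higher event. This assumes that all 8 were recorded under the Section 7.8.6 rule. The rate under Section 7.8.1 would be (38 - d)/133.

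| d | Rate under Section 7.8.1 | Exact 95% CI |
|---|---|---|
| 0 | 38/133 = 28.6% | 21.1% to 37.0% |
| 4 | 34/133 = 25.6% | 18.4% to 33.8% |
| 8 | 30/133 = 22.6% | 15.8% to 30.6% |

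The gap is d/133, from 0 to 6.0 percentage points. The documents do not give d. Other laboratory terms could add to the gap, but the protocol does not give their Grade 3 or higher related rates.

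**The case against.** **The conflicting group may be small, and this stands.** Other protocol rules make many severe laboratory values meet a Section 7.8.1 trigger. Sections 6.5.2.2.1 and 6.5.2.2.2 generally call for discontinuation at Grade 3 or 4 transaminase or bilirubin elevation. Section 7.8.2.6 requires values meeting potential Hy's law criteria to be reported within 24 hours. Section 4.5.1 calls for study drug to be held while a potentially dose-limiting toxicity is assessed, so even a lipase rise may involve an interruption. What remains is not sized in the documents, and the range in the working properly includes zero.

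**Nothing shows that events were lost, and this also stands.** The interim data report lipase increased, and lymphocyte count decreased (5.3%), as AEs. Section 10 provides for training on the eCRFs, monitoring and queries. A reader might infer that both rules have been applied, or that the true rate exceeds 28.6%. The documents show only that either could happen.

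**Section 7.8.1 may be no more than a warning against duplicate entry. This does not stand.** Its next sentence is an outright restriction with a closed list. In Section 7.8.6 the closing qualifier chooses between AE and SAE; it does not make reporting optional.

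**Shift tables are partly a matter of preference.** They would be an improvement in any case. Here they have a further use, because they give a count by grade that does not depend on which reporting rule a site followed.

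**Conclusion.** The protocol contradicts itself, and the SAP sides with Section 7.8.6. The Grade 3 or higher and drug-related Grade 3 or higher AE summaries can therefore vary by site for non-serious Grade 3 or 4 laboratory values with no treatment change and no intervention. This is an internal inconsistency that should be fixed.

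The shift of 0 to 6.0 points is an illustration. Its upper end requires all 8 lipase patients to have met no trigger and to have had no other related Grade 3 or higher event, and Section 2.3.1.1.2 gives no information on either condition.

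Three stronger readings are tempting but not supported:

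- **A primary endpoint is compromised.** No Grade 3 or higher AE rate is named as primary. The primary objectives are safety, tolerability, DLT and, for the pembrolizumab combination, MTD or MAD. These tables are among several descriptive summaries that support them.
- **The MTD or MAD is in doubt.** DLTs count laboratory abnormalities directly, so on the text it is not.
- **Cohort 4 will differ from the pembrolizumab cohorts because of reporting.** The same two texts govern every cohort, no mechanism for a difference is given, and no formal comparison between cohorts is planned.

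**What to change.** **1. SAP 6.7.2 (the more important change).** Replace "Shift tables may be generated" with: *CTCAE-grade shift tables (baseline to worst post-baseline grade) will be generated from laboratory values for each cohort.* Section 2.3.1.1.2 states that the pembrolizumab cohorts are closed to enrolment and that their patients have completed combination treatment, so new protocol wording cannot by itself change how their AEs were reported. Tables built from the values apply one definition to those cohorts and to Cohort 4. The values are already collected, and Section 7.8.6 already provides for CTCAE v4.03 grading. These tables carry no causality assessment, so they complement the drug-related AE table and do not repair it.

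**2. Protocol Section 7.8.1 and synopsis.** Add to the trigger list: *or is Grade 3 or 4, or is judged clinically significant (Section 7.8.6)*. Align the preceding sentence on double reporting, so that it no longer discourages an AE entry that Section 7.8.6 requires. State in the study report that this wording changed after the pembrolizumab cohorts closed.

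**Cost.** A short amendment to the protocol, one SAP sentence and slightly more programming. The reported Grade 3 or higher rate may become slightly less favourable. The protocol change would mainly govern Cohort 4, planned at up to 15 patients. On its own it could create a reporting difference from the earlier cohorts, which is why the SAP change should accompany it.
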